NCT05105477

**Hypotension Prediction Index Software Guided
Hemodynamic Management for Noncardiac Surgery
Patients - Blood Pressure Trial –**

HPI SMART- BP Trial

**A Multicenter, Interventional, Randomized comparison of intraoperative hemodynamic
management with or without Hypotension Prediction Index software guidance on postoperative
complications**

Clinical Trial Protocol and Statistical Analysis Plan

Clinical Trial Protocol version: December 17, 2021

Statistical Analysis Plan version: May 11, 2022

Hypotension Prediction Index Software Guided Hemodynamic Management for Noncardiac Surgery Patients - Blood Pressure Trial

HPI SMART- BP Trial

A Multicenter, Interventional, Randomized comparison of intraoperative hemodynamic management with or without Hypotension Prediction Index software guidance on postoperative complications

Clinical Trial Protocol
Trial Number: 2021-04

Revision: C
Date: 17DEC21

Edwards Lifesciences LLC
[name]
[name]

THIS DOCUMENT CONTAINS CONFIDENTIAL AND PROPRIETARY INFORMATION OF EDWARDS LIFESCIENCES, LLC. IT MAY NOT BE REPRODUCED OR DISCLOSED WITHOUT PRIOR WRITTEN PERMISSION FROM EDWARDS LIFESCIENCES, LLC.
Edwards Lifesciences, Edwards, the stylized E logo, HemoSphere, Acumen, Acumen IQ, FloTrac, and ForeSight Elite oximetry Sensor are trademarks of Edwards Lifesciences Corporation.

Revision B Change Summary

Please note: Punctuation, formatting or clerical changes are not included in the table.

Section (Page)	Change and Reason for Change
Synopsis and Trial Objective (7 & 17)	Updated trial objective to the following: To determine if the use of a protocolized strategy using advanced hemodynamic monitoring with Hypotension Prediction Index (HPI) software guidance for intraoperative hemodynamic management reduces postoperative complication rate in moderate- to high-risk non-cardiac surgery.” Reason: To provide further clarification.
Synopsis, Background & General Design (7,10 & 23)	Added “The control arm will be blinded to advanced hemodynamic monitoring with and will only receive blood pressure monitoring data from the arterial line, as per the standard of care.” Reason: To provide further clarification for control arm design.
Synopsis, Procedure, and Sample size Justification (7, 35 & 37)	Updated total enrollment to 1486 Reason: To align with statistical analysis plan.
Synopsis, Additional Evaluation (Trial Objective and Endpoints) Additional Evaluation (Statistical Methods) (8,17 & 38)	Updated item 9 to following: Amount of vasoactive drugs; mg (e.g.: phenylephrine, ephedrine, norepinephrine, epinephrine, dobutamine) Added item 10: Amount of intraoperative intravenous analgesics and sedatives Added item 12: Verification of the incidence of the listed postoperative complications may be performed at each site by reviewing historic data up to 6 months prior to study initiation. Reason: To provide further clarification.
Synopsis and Treatment Protocol (8 &24)	Edited Alert phase to state: HPI greater than 85 → alert → treatment per protocol recommendation Edited treatment protocol's figure to display the targeted treatment plan. Reason: To provide further clarification.
Schedule of Events (34)	Added footnote for Creatinine labs to be collected on post-op day 1,2 or 3. Reason: To provide further clarification.

THIS DOCUMENT CONTAINS CONFIDENTIAL AND PROPRIETARY INFORMATION OF EDWARDS LIFESCIENCES, LLC. IT MAY NOT BE REPRODUCED OR DISCLOSED WITHOUT PRIOR WRITTEN PERMISSION FROM EDWARDS LIFESCIENCES, LLC.

Edwards Lifesciences, Edwards, the stylized E logo, HemoSphere, Acumen, Acumen IQ, FloTrac, and ForeSight Elite oximetry Sensor are trademarks of Edwards Lifesciences Corporation.

Revision C Change Summary

Please note: Punctuation, formatting or clerical changes are not included in the table.

Section (Page)	Change and Reason for Change
Synopsis & Treatment Protocol (9 & 24)	Added “Clinicians should validate the appropriateness of protocol recommendations, and provide treatment based upon their clinical judgment.” Reason: To provide further clarification that clinical judgement is key to treatment.
Additional Evaluations (17 & 39)	Added additional datapoints for analysis Reason: Sensitivity analysis for any missing 30-Day follow-up and treatment protocol compliance analysis
Synopsis, Schema, Schedule of Events & Procedures (10, 27,32)	Removed MoCA; Added: Pre-op Surgical Risk Assessment, Post-Op Neurocognitive Assessments Reason: Change in assessment type
General Design (24)	Added “The HPI Pressure & Flow Optimization Protocol provides recommendations for treatment. Clinicians are instructed to validate the appropriateness of protocol recommendations, and provide treatment based upon their clinical judgment” Reason: Clarification on non-significant risk reasons.
Randomization and Blinding (25)	Changed “Study investigators and staff will be blinded up until the time of the surgery. The staff member(s) involved in the consenting of the patient will be blinded to the randomization assignment and will not be involved in the care of the Trial subject.” to “Study investigators will be blinded up until the time of the surgery. The clinician(s) involved in the consenting of the patient will be blinded to the randomization assignment and will not be involved in the care of the Trial subject.” Reason: To clarify the randomization and blinding.
Roll-in Subjects (30)	Updated the roll-ins to a max of 5 at a site. The total roll-in cases remain at 60. Reason: To allow for additional roll-in cases at sites that need them.
Procedure (35)	Added “Interventions conducted per treatment protocol and/or outside the treatment protocol will be documented on the eCRF(s). Clinicians should validate the appropriateness of protocol recommendations, and provide treatment based upon their clinical judgment.” Reason: To clarify the intervention data that will be collected.
Additional Evaluations (39)	Added “Sensitivity analysis including the review of any influence of surgical position, type of anesthesia, tidal volume etc., on the primary outcome measure, are specified in the SAP.” Reason: Clarification on sensitivity analysis.
Anticipated Risks (42)	Added risks related to associated with HPI Pressure and Flow Optimization Protocol Reason: To clarify risks that may be associated with treatment protocol.

THIS DOCUMENT CONTAINS CONFIDENTIAL AND PROPRIETARY INFORMATION OF EDWARDS LIFESCIENCES, LLC. IT MAY NOT BE REPRODUCED OR DISCLOSED WITHOUT PRIOR WRITTEN PERMISSION FROM EDWARDS LIFESCIENCES, LLC.

Edwards Lifesciences, Edwards, the stylized E logo, HemoSphere, Acumen, Acumen IQ, FloTrac, and ForeSight Elite oximetry Sensor are trademarks of Edwards Lifesciences Corporation.

STATEMENT OF COMPLIANCE

INVESTIGATOR'S SIGNATURE PAGE

This trial will be carried out in accordance with the protocol, International Conference on Harmonisation Good Clinical Practice (ICH GCP), applicable state, local and federal regulatory requirements as well as 45 CFR Part 46, 21 CFR Parts 11, 50, 54, 56 and 812.

Trial Objective:	To determine if the use of a protocolized strategy using advanced hemodynamic monitoring with Hypotension Prediction Index (HPI) software guidance for intraoperative hemodynamic management reduces postoperative complication rate in moderate- to high-risk non-cardiac surgery.
Primary Effectiveness Endpoint:	The primary hypothesis is that the administration of advanced hemodynamic monitoring utilizing the Hypotension Prediction Index (HPI) with a protocolized strategy during moderate-to-high-risk noncardiac surgery reduces composite of severe postoperative complications at 30 days. The composite includes: Major adverse cardiac events MACE (myocardial injury, stroke, non-fatal cardiac arrest, and death), acute kidney injury (AKI), and serious infection. Specifically, we seek to evaluate if the treatment protocol utilizing the technology from Edwards Lifesciences will result in a relative change of at least 25% in the composite complication score when compared to the control arm that will receive an arterial line with only blood pressure monitoring, as per the standard of care.
Trial Devices:	HemoSphere Advanced Monitor, Acumen™ HPI Feature Software, Acumen IQ sensor, FloTrac sensor, and ForeSight Elite Oximetry sensor.
Overall Design:	A multicenter, randomized comparison of intraoperative hemodynamic management with or without a protocolized strategy utilizing Hypotension Prediction Index (HPI) software guidance during moderate-to-high-risk noncardiac surgery.
Trial Population:	Up to 1486 adults undergoing moderate-to-high-risk noncardiac surgery who will be receiving pressure monitoring with an arterial line.
Number of Sites:	Up to Twenty (20) U.S. Sites
Trial Duration:	Total of 24 to 36 months
Participation Duration:	Screening/Baseline; Procedure; Post-Op Days 1-3; ICU; hospital discharge; 30-day Telephone Follow-Up Visit
Inclusion/Exclusion Criteria	Inclusion Criteria: 
1. Signed informed consent;2. Age \geq 18 years;

THIS DOCUMENT CONTAINS CONFIDENTIAL AND PROPRIETARY INFORMATION OF EDWARDS LIFESCIENCES, LLC. IT MAY NOT BE REPRODUCED OR DISCLOSED WITHOUT PRIOR WRITTEN PERMISSION FROM EDWARDS LIFESCIENCES, LLC.

Edwards Lifesciences, Edwards, the stylized E logo, HemoSphere, Acumen, Acumen IQ, FloTrac, and ForeSight Elite oximetry Sensor are trademarks of Edwards Lifesciences Corporation.

3. ASA Physical Status \geq 2;
4. Noncardiac surgery with expected surgery duration \geq 2 hours (example include: orthopedic, spine, urology, and general surgery)
5. Planned blood pressure monitoring with an arterial line catheter;
6. General anesthesia;

Exclusion Criteria:

1. Participating in another interventional Trial;
2. Contraindication to arterial blood pressure monitoring;
3. Subjects with a physical site area too limited for proper Sensor placement
4. Serum creatine $> 175 \mu\text{mol/L}$ ($> 2.0 \text{ mg/dL}$) or CKD stage $> 3A$
5. Scheduled for intracranial surgery with permissive hypotension;
6. Patient who is confirmed to be pregnant and/or nursing mothers;
7. Patients with an intra-aortic balloon pump (IABP) or ventricular assist device(s);
8. Have a condition that precludes routine or tight blood pressure management such as surgeon request for relative hypotension;
9. Emergency surgery;
10. Require beach-chair positioning;
11. Scheduled for cardiac surgeries
12. Have previously participated in the SMART-BP trial.

Alert Phase: HPI greater than 85 \rightarrow alert \rightarrow treatment per protocol recommendation

Treatment Protocol: Monitoring Phase: HPI 50 – 85 \rightarrow evaluate flow / vascular tone indices and fluid responsive state.

Clinicians should validate the appropriateness of protocol recommendations, and provide treatment based upon their clinical judgment.

A composite of 30-day moderate-to-severe perfusion related postoperative complications. The composite includes:

Primary Outcome:

1. MACE (myocardial injury, stroke, non-fatal cardiac arrest, and death)
2. Acute kidney injury (KDIGO stage 2-3)
3. Serious Infections: pneumonia, deep surgical site or organ space infections, and sepsis

Preoperative Assessments: Creatinine, Surgical Risk Assessment (NSQIP¹), Troponin, NT-proBNP

THIS DOCUMENT CONTAINS CONFIDENTIAL AND PROPRIETARY INFORMATION OF EDWARDS LIFESCIENCES, LLC. IT MAY NOT BE REPRODUCED OR DISCLOSED WITHOUT PRIOR WRITTEN PERMISSION FROM EDWARDS LIFESCIENCES, LLC.

Edwards Lifesciences, Edwards, the stylized E logo, HemoSphere, Acumen, Acumen IQ, FloTrac, and ForeSight Elite oximetry Sensor are trademarks of Edwards Lifesciences Corporation.

Postoperative Assessments: Troponin and Post-Op delirium assessment POD 1,2,3; Creatinine POD 2, Post-Operative Morbidity Survey (POMS⁷) POD 3, 30-day Follow-up, World Health Organization Disability Assessment Schedule 2.0 (WHODAS 2.0¹⁹)

Trial Sponsor: Edwards Lifesciences LLC
[name]

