Throughout the Trial, the randomization assignment will remain blinded to all parties, with the study investigators and staff being blinded up until the time to surgery. Randomization assignment can be unblinded in the case of a medical emergency that requires the treatment assignment to be known. In this case, an individual subject blind may be broken via the Code Break Module by the Investigator or Medical Reviewer. When possible, the Investigator is to consult with the Medical Reviewer, or designee, prior to breaking the code. The Investigator is to capture the date, time, and reason for breaking the blind in the subject's source notes. Additionally, an independent biostatistician will be unblinded to the randomization codes in order to conduct the interim analysis. All other parties will be blinded to the randomization at time of the interim. After completion of the Trial, the randomization codes will be unblinded, post database lock and with the Trial Sponsor's approval to unblind.

THIS DOCUMENT CONTAINS CONFIDENTIAL AND PROPRIETARY INFORMATION OF EDWARDS LIFESCIENCES, LLC. IT MAY NOT BE REPRODUCED OR DISCLOSED WITHOUT PRIOR WRITTEN PERMISSION FROM EDWARDS LIFESCIENCES, LLC.

Edwards Lifesciences, Edwards, the stylized E logo, HemoSphere, Acumen, Acumen IQ, FloTrac, and ForeSight Elite oximetry Sensor are trademarks of Edwards Lifesciences Corporation.

[figure not shown]
Schema

Figure 2 Enrollment Flow Diagram

THIS DOCUMENT CONTAINS CONFIDENTIAL AND PROPRIETARY INFORMATION OF EDWARDS LIFESCIENCES, LLC. IT MAY NOT BE REPRODUCED OR DISCLOSED WITHOUT PRIOR WRITTEN PERMISSION FROM EDWARDS LIFESCIENCES, LLC.
Edwards Lifesciences, Edwards, the stylized E logo, HemoSphere, Acumen, Acumen IQ, FloTrac, and ForeSight Elite oximetry Sensor are trademarks of Edwards Lifesciences Corporation.

Figure 3 Enrollment Timeline Diagram

*Roll-ins not included.

THIS DOCUMENT CONTAINS CONFIDENTIAL AND PROPRIETARY INFORMATION OF EDWARDS LIFESCIENCES, LLC. IT MAY NOT BE REPRODUCED OR DISCLOSED WITHOUT PRIOR WRITTEN PERMISSION FROM EDWARDS LIFESCIENCES, LLC.
Edwards Lifesciences, Edwards, the stylized E logo, HemoSphere, Acumen, Acumen IQ, FloTrac, and ForeSight Elite oximetry Sensor are trademarks of Edwards Lifesciences Corporation.

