Monitoring Duration			X					
Data download from Monitor ³			X					
Obtain Fluid and Vasoactive Medication Administration Record ²			X	X				
Obtain post-operative complications, if applicable			X	X	X	X	X	X
Labs: Creatinine ⁴		X			X			
Labs: Troponin		X		X	X	X		
Labs: NT-proBNP		X						
POMS ⁵						X		
NSQIP Surgical Risk Assessment ⁵		X						
Post-Op delirium assessment (e.g., 4AT or 3D-CAM) ⁵				X	X	X		
WHODAS 2.0 ⁵								X
Complete eCRFs	X	X	X	X	X	X	X	X
Record Adverse Events, if applicable			X	X	X	X	X	X
Obtain ICU / Hospital discharge Information							X	X
Phone Contact 30-day follow up / Mortality Determination								X

¹ Medical History / Subject Demographics / Surgical and Clinician Demographics can be obtained prior to procedure, either at the screening visit or on the day of procedure.

² Can be collected via the hospital record system anytime on the day of procedure or thereafter.

³ To be conducted for subjects assigned to treatment arm

⁴ To be collected on post-op day 1, 2 or 3.

⁵ To be collected if data or subject is available.

THIS DOCUMENT CONTAINS CONFIDENTIAL AND PROPRIETARY INFORMATION OF EDWARDS LIFESCIENCES, LLC. IT MAY NOT BE REPRODUCED OR DISCLOSED WITHOUT PRIOR WRITTEN PERMISSION FROM EDWARDS LIFESCIENCES, LLC.

Edwards Lifesciences, Edwards, the stylized E logo, HemoSphere, Acumen, Acumen IQ, FloTrac, and ForeSight Elite oximetry Sensor are trademarks of Edwards Lifesciences Corporation.

Procedure

The HPI SMART-BP Trial will collect data from up to 1486 subjects at up to 20 study sites across the United States. Up to 60 subjects may be included as roll-ins and will be analyzed separately from the pivotal cohort. Subjects will be randomly assigned to the interventional or control arms. The maximum number of subjects enrolled at each site will not exceed 20% of the total study population.

A subject will be considered enrolled in the Trial once the subject has signed the informed consent, has been assigned a Trial ID, an arterial line with either a FloTrac sensor (control arm) or Acumen IQ sensor (treatment arm) has been connected. Subjects may be screened for eligibility and consented on the day of surgery.

Subject participation will include preoperative study eligibility screening and consent, planned surgical intervention, Post-Op Day 1-3, ICU, hospital discharge, and 30 days post-procedure. Discontinued subject data will be analyzed under intent-to-treat and data will be used for safety and performance analyses.

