7. STATISTICAL METHODS

Statistical Analysis Plan (SAP)

There will be a formal SAP, separate from this Trial protocol. A formal SAP will be completed prior to database lock and the analysis of any Trial endpoints data. The SAP will detail the planned statistical analyses. The subsections below summarize the planned analyses.

Primary Outcome Endpoint

The primary outcome endpoint is to determine if the use of a protocolized strategy using advanced hemodynamic monitoring with Hypotension Prediction Index (HPI) software guidance for intraoperative hemodynamic management reduces postoperative complication rate in moderate- to high-risk non-cardiac surgery. The composite includes MACE (myocardial injury, stroke, non-fatal cardiac arrest, and death), AKI, and serious infections (pneumonia, deep and organ space surgical site infections, and sepsis).

THIS DOCUMENT CONTAINS CONFIDENTIAL AND PROPRIETARY INFORMATION OF EDWARDS LIFESCIENCES, LLC. IT MAY NOT BE REPRODUCED OR DISCLOSED WITHOUT PRIOR WRITTEN PERMISSION FROM EDWARDS LIFESCIENCES, LLC.
Edwards Lifesciences, Edwards, the stylized E logo, HemoSphere, Acumen, Acumen IQ, FloTrac, and ForeSight Elite oximetry Sensor are trademarks of Edwards Lifesciences Corporation.

Sample Size Justification

The goal of this study is to assess if the use of Hypotension Prediction Index (HPI) software guidance impacts the incidence of postoperative morbidity and mortality in the adult population undergoing moderate-to-high-risk noncardiac surgery (with a pressure monitoring with an arterial line). A relative reduction in the composite outcome within the treatment arm is expected. For a group sequential analysis, following the O'Brien and Fleming methodology, a sample size was calculated for a two-sample comparison of rates (two-sided). The hypothesis are as follows:

$$H_0: p_0 - p_1 \geq 0$$

$$H_1: p_0 \neq p_1$$

Assuming at least a 25% relative change in rate for the treatment (p_1) arm, a type I error (0.05), a power of 80%, and a reference rate of 0.31 (p_0) based on a meta-analysis^{6,10,14}, a sample size of 1426 subjects are needed. An additional 60 subjects may be included as roll-ins, which results in a total enrollment potential of 1486 subjects.

Analysis Populations

Modified Intent-to-treat (mITT)

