Assuming a power of 80% and a relative reduction of at least 25% in the composite score (reference proportion=0.31) with three total looks (two interim analysis, one final), the critical values for each time point were chosen to preserve an overall type-1 error rate of 0.05. The O'Brien and Fleming methodology was used to determine the boundary rule for deciding when to stop the trial prematurely. Futility was included. A relative reduction in the composite outcome within the treatment arm is expected. The alpha at each interim and the maximum number of observations are chosen so that the overall significance level is the probability of detecting the treatment difference under the null hypothesis. The table below shows the critical values:

Analysis	Information Rate	Effectiveness Boundary z-value (Upper, Lower)	Futility Boundary z-value (Upper, Lower)
First Interim Analysis	50%	(2.96259, -2.96259)	(0.40273, -0.40273)
Second Interim	75%	(2.35898, -2.35898)	(1.12741, -1.12741)
Final Analysis	100%	(2.01404, -2.01404)	(2.01404, -2.01404)

THIS DOCUMENT CONTAINS CONFIDENTIAL AND PROPRIETARY INFORMATION OF EDWARDS LIFESCIENCES, LLC. IT MAY NOT BE REPRODUCED OR DISCLOSED WITHOUT PRIOR WRITTEN PERMISSION FROM EDWARDS LIFESCIENCES, LLC.

Edwards Lifesciences, Edwards, the stylized E logo, HemoSphere, Acumen, Acumen IQ, FloTrac, and ForeSight Elite oximetry Sensor are trademarks of Edwards Lifesciences Corporation.

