14. CHANGES TO THE PROTOCOL

Changes to the research covered by this protocol must be implemented by formal protocol amendment. All amendments to the protocol must be initiated by the Sponsor.

Protocol amendments must not be implemented without prior IRB approval. Documentation of amendment approval by the Investigator and IRB or IEC must be provided to the Sponsor or its authorized representative. When the change(s) involve only logistic or administrative aspects of the Trial, the IRB only needs to be notified.

THIS DOCUMENT CONTAINS CONFIDENTIAL AND PROPRIETARY INFORMATION OF EDWARDS LIFESCIENCES, LLC. IT MAY NOT BE REPRODUCED OR DISCLOSED WITHOUT PRIOR WRITTEN PERMISSION FROM EDWARDS LIFESCIENCES, LLC.

Edwards Lifesciences, Edwards, the stylized E logo, HemoSphere, Acumen, Acumen IQ, FloTrac, and ForeSight Elite oximetry Sensor are trademarks of Edwards Lifesciences Corporation.

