By the study designed parameter table in section 2.3 and the Z statistic calculated at each study stage with the trial data collected at present stage in addition to data collected in previous stage or stages, following judgement will be conducted for interim analysis and final analysis. For first and second interim analyses, if the calculated Z value is equal to or less than the critical Z value in the effectiveness boundary column, the null hypothesis will be rejected, and the study will stop for achieving the study objective; if the calculated Z statistic is greater than critical Z value for effectiveness but it is close to the critical value but could not reject null hypothesis, the study continues to next step, and the study sample seize will be reassessed by the principles of adapted group sequential study design. If it is necessary, more study subject will be enrolled for the purpose to achieve the study objectives. For final analysis, if the calculated Z statistic is equal to or less than the critical Z value listed in effectiveness boundary column, the null hypothesis will be rejected, and the alternative hypothesis will accept, the study objective is achieved, otherwise, the null hypothesis will accept, the study objective will be not achieved.

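### Protocol and SAP disagree on the maximum sample size: the protocol stops at 1,486, while the SAP allows an unblinded increase with no stated ceiling and no route that avoids a mid-trial amendment

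*Combined protocol and SAP*

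**What the plan says.** **Protocol.** The ceiling appears three times. The synopsis gives "Up to 1486 adults undergoing moderate-to-high-risk noncardiac surgery who will be receiving pressure monitoring with an arterial line". Section 6 (Procedure) says "The HPI SMART-BP Trial will collect data from up to 1486 subjects at up to 20 study sites across the United States". Section 7 (Sample Size Justification) builds the figure: "a sample size of 1426 subjects are needed", and 60 roll-ins may be added, "which results in a total enrollment potential of 1486 subjects". Section 7 (Planned Interim Analyses) describes two interims and a final analysis with efficacy and futility bounds, and ties the maximum to the error rate: "The alpha at each interim and the maximum number of observations are chosen so that the overall significance level" is preserved. Nowhere does it provide for re-estimating the sample size.

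**SAP.** Section 2.2 describes an adaptive group-sequential design in which an independent, unblinded third-party statistician may reassess the sample size. Sections 2.2, 2.3 and 8.1 make the criterion closeness of Z to the efficacy boundary without crossing it, and 8.1 applies this at both interims: "If it is necessary, more study subject will be enrolled for the purpose to achieve the study objectives". No ceiling, numerical zone, formula or modified test is given. Section 10 says the protocol-specified analyses are unchanged.

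**Governance.** Protocol Section 14 requires a formal amendment with prior IRB approval for changes to the research, and "All amendments to the protocol must be initiated by the Sponsor". Section 4 says of the interim: "All other parties will be blinded to the randomization at time of the interim". Section 10 has the DSMB base its recommendations on continuing the trial on safety alone.

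**The concern.** The largest size a trial may reach is a core design parameter, and here it has two answers. The protocol's is 1,486. The SAP's is open.

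If the SAP's option were used beyond 1,486, the increase would reach the sponsor as an instruction to amend, after a look at unblinded data. The only criterion stated for an increase is nearness to the efficacy boundary. A sponsor that knows the SAP and is asked for more subjects could infer that the trend favours the HPI arm and that the boundary was not crossed.

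That matters in this trial because allocation is known once surgery starts (SAP 2.4), control-arm management is left to the anesthesia team (protocol Section 6), and parts of the composite need judgement, such as attributing a raised troponin to ischemia (protocol Section 3). This is a separate matter from whether re-estimation needs an alpha adjustment. A statistically valid re-estimation would still exceed the protocol's ceiling and would still lack a communication route.

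**Working it through.** **1. The ceiling.** 1,426 + 60 = 1,486, which agrees with the protocol. The 1,426 itself is larger than 80% power requires (fixed design 1,032; with the printed efficacy bounds 1,054; with futility as well 1,104; with futility and 15% attrition 1,299). That is a different issue and does not affect this point.

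**2. The two documents side by side.**

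| Item | Protocol | SAP |
|---|---|---|
| Starting total | 1,486 | 1,486 |
| Re-estimation | none | yes, unblinded |
| Trigger | none | Z close to the efficacy boundary, not quantified |
| Maximum after an increase | none above 1,486 | not stated |
| Declared change from protocol | n/a | none |

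**3. Does the trigger pick out trials that need more subjects?** Inputs: efficacy bounds 2.96259 and 2.35898, final bound 2.01404, information fractions t = 0.50 and 0.75 (protocol Section 7; SAP 2.3). Z is taken in the direction of benefit. Conditional power at the planned 1,426, under the observed trend and counting only the final test, is

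CP = Φ[(Z/√t − 2.01404)/√(1 − t)].

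The SAP does not define *close*. For illustration I take a point about 0.5 below each boundary, and the boundary itself.

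- Look 1, Z = 2.46: (3.479 − 2.014)/0.707 = 2.07, CP ≈ 98%.
- Look 1, Z = 2.963: (4.190 − 2.014)/0.707 = 3.08, CP ≈ 99.9%.
- Look 2, Z = 1.86: (2.148 − 2.014)/0.5 = 0.27, CP ≈ 61%.
- Look 2, Z = 2.359: (2.724 − 2.014)/0.5 = 1.42, CP ≈ 92%.

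At look 1 the trigger points to trials that hardly need more subjects. At look 2 an increase could add power.

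**4. What an uncapped rule could imply.** Assume a rule that raises N until conditional power under the observed trend reaches 80% (an assumption, since the SAP gives no rule). At look 1 this calls for an increase only when Z < (2.01404 + 0.8416 × 0.7071)/1.4142 = 1.84, well below the boundary. With 713 subjects at look 1, the total N is then 1,519 at Z = 1.8, 2,016 at 1.6, 2,726 at 1.4 and 5,591 at 1.0. Each exceeds 1,486.

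Simulating this uncapped rule with the unadjusted statistic gave a one-sided error of 0.0277 if any Z above 0.4 triggers an increase, 0.0255 above 0.8, and about 0.025 or less above 1.2. Error control therefore depends on the undefined zone.

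**5. What is lost without the option.** Power is the probability that a trivariate normal crosses 2.96259, 2.35898 or 2.01404, with drift (p0 − p1)/√[(p0(1 − p0) + p1(1 − p1))/713] and 713 per arm. The bounds return a one-sided alpha of 0.0250.

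- 0.31 vs 0.2325 (25% reduction): drift 3.30, power 91%.
- 0.31 vs 0.248 (20% reduction): drift 2.62, power 74%.
- 0.20 vs 0.15 (25% reduction): drift 2.49, power 69%.

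**The case against.** The protocol says its statistical section is a summary and that the SAP supplies the detail, so the SAP might be taken to govern. That holds for analyses, but an enrolment ceiling is not an analysis, and deferring to the SAP does not lift it.

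Several stronger readings are tempting and do not stand:

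- *The SAP's instruction cannot be carried out.* Section 14 of the protocol provides an amendment route, so an increase is possible. The difficulty is its timing.
- *An increase would breach the interim blinding.* The sentence in Section 4 concerns the randomization and follows one about randomization codes. Telling the sponsor a new N does not reveal codes, and SAP 2.2 says the independent statistician will not unblind the study statistician.
- *An amendment would disclose a specific observed effect.* Working that out needs a defined trigger zone and the observed control rate. The documents give no zone, and an amendment would not show the rate. The zone in the working is mine.
- *The SAP permits unlimited enrolment.* No limit is printed, but up to 20 sites and 24 to 36 months are practical bounds.
- *The option is unnecessary because power is already about 90%.* That holds only at the assumed rate and effect. Re-estimation protects against those being wrong, and the SAP's own composite estimates run from 0.2962 to 0.6007.

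**Conclusion.** The inconsistency stands. The documents give different answers on the maximum sample size, and the SAP's reassessment has no ceiling, no quantified trigger and no route that avoids a sponsor amendment after an unblinded look. It should be resolved before the first interim.

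That an increase would signal a favourable trend to the sponsor is an inference. It is sound in direction, because nearness to the efficacy boundary is the only criterion given. Its precision depends on the undefined zone, and spread to sites is possible but not certain. No size of resulting bias can be derived from the documents.

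The poor fit of the trigger at look 1 rests on conditional power under the observed trend and on reading *close* as within about 0.5 of the boundary. Whether to keep re-estimation is a design choice for the sponsor.

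**What to change.** Make the two documents agree before the first interim, in one of two ways.

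1. **Keep the option.** Put into both documents one numerical maximum N, a numerical trigger zone and re-estimation rule, and the test that controls alpha. Have the independent statistician and the DSMB hold the rule, and state who is told what after each look, so that no amendment is needed after unblinded data are seen. Reconcile this with the DSMB's safety-only recommendation role in protocol Section 10, and list the change in SAP 10. Cost: one protocol amendment and one SAP revision. Sponsor and sites would still see enrolment pass 1,426, so some signal remains; a trigger zone known only to those two parties would blunt it.

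2. **Drop the option.** Remove the reassessment wording from SAP 2.2, 2.3 and 8.1, keep 1,426 plus up to 60 roll-ins as the maximum, and let a near-boundary interim continue to the next look. Cost: a few SAP edits, and the loss of protection against a lower event rate or smaller effect shown in step 5 of the working.
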